1 GLOSSARY OF ABBREVIATIONS

Abbreviation	Description
5-HIAA	5-hydroxyindoleacetic acid
AE	Adverse event
ATC	Anatomical Therapeutic Chemical
CgA	Chromogranin A
CL	Confidence limit
eCRF	Electronic case report form
CS	Carcinoid syndrome
DSMB	Data Safety Monitoring Board
ECG	Electrocardiogram
EOS	End of study
EORTC	European Organisation for Research and Treatment of Cancer
ICH	International Conference on Harmonisation
LP-778902	Active moiety of LX1606
LS	Least square
LX1606	Telotristat ethyl, (the ethyl-ester prodrug of the active moiety LP-778902); a serotonin synthesis inhibitor being developed by Lexicon Pharmaceuticals, Inc.
MedDRA	Medical Dictionary for Regulatory Activities
MMRM	Mixed model with repeated measurement
NET	Neuroendocrine tumor
NRS	Numeric rating scale
PP	Per-protocol
PT	Preferred term
QoL	Quality of life
QLQ	Quality of life questionnaire
QTc	Corrected QT interval

Lexicon Pharmaceuticals, Inc.
[name]
[name]

1003157

Lexicon Pharmaceuticals, Inc.

LX1606.302

Final V1.0

Statistical Analysis Plan

Abbreviation	Description
QTcF	Corrected QT interval using Fridericia's formula
SAE	Serious adverse event
SAF	Safety population
SAP	Statistical analysis plan
SD	Standard deviation
SI	Standard international system of units
SOC	System organ class
SOP	Standard operating procedure
TEAE	Treatment-emergent adverse event
tid	3 times daily
TLFs	Tables, listings and figures
ULN	Upper limit of normal

Statistical Analysis Plan

2 PURPOSE

The purpose of this statistical analysis plan (SAP) is to ensure that the data listings, summary tables, and figures which will be produced, and the statistical methodologies that will be used, are complete and appropriate to allow valid conclusions to be drawn regarding the study objectives.

2.1 RESPONSIBILITIES

INC Research will perform the statistical analyses and are responsible for the production and quality control of all analysis datasets, tables, listings, and figures (TLFs).

2.2 TIMINGS OF ANALYSES

The study will be analyzed and reported in 2 phases. The first report will summarize data obtained from all patients providing information up to a specified data cut-off point. The second report will update the initial report by including data from the remaining portion of the study. The first reporting of the data may be taken as an interim analysis in terms of the procedural efforts needed to summarize these data, but it will not serve as a means to modify the analysis/study conduct.

An independent Data Safety Monitoring Board (DSMB) will be charged with reviewing interim safety data on a quarterly basis and reporting its recommendations to Sponsor. Appropriate procedures will be detailed in a DSMB charter that defines accessibility and disclosure of the interim safety results.

3 STUDY OBJECTIVES

3.1 PRIMARY OBJECTIVE

The primary objective of the study is to evaluate the long-term safety and tolerability of orally administered telotristat etiprate.

3.2 SECONDARY OBJECTIVES

The secondary objective of this study is to evaluate long-term changes in patients' quality of life (QoL).

3.3 SAFETY OBJECTIVES

Evaluation of overall safety will be assessed as:

- Incidence of treatment-emergent adverse events (TEAEs)

1003157

Lexicon Pharmaceuticals, Inc.

LX1606.302

Final V1.0

Statistical Analysis Plan

- Changes from Baseline in clinical laboratory results, vital signs results, and electrocardiogram (ECG) findings

4 STUDY DESIGN

4.1 BRIEF DESCRIPTION

This is a Phase 3, multicenter, open-label, long-term extension study to further evaluate long-term safety and tolerability of telotristat etiprate for patients with carcinoid syndrome (CS).

Patients currently participating in any LX1606 Phase 2 CS study may enter into this extension study upon institutional or local approval of the protocol. Patients participating in a Phase 3 CS study may enter into this extension study at the Week 48 visit. All patients who enter into this extension study will be exempt from any Follow-up visit required by the original study and will not experience an interruption in study drug due to the transition from the original protocol to LX1606.1-302-CS.

Following confirmation of eligibility, patients will complete a series of visit assessments in order to establish baseline symptoms. Patients will then continue on open-label LX1606 at the dose level specified in the original study.

Downward dose adjustment will be permitted during the study if evidence of intolerability emerges. Patients who experience intolerability at the telotristat etiprate 250 mg (as free base) tid dose level must be discontinued from the study. Patients may return to their previous dosing at the discretion of the Investigator and in consultation with the Medical Monitor.

Upon completion or early withdrawal from treatment, all patients will be required to complete a 14-day Follow-up Period, during which no study drug will be administered.

A DSMB will review safety data quarterly throughout the study.

4.2 PATIENT SELECTION

Adult patients who are currently participating in ongoing Phase 2 or Phase 3 telotristat etiprate CS clinical protocols will be enrolled into the study. Up to 100 patients are expected to enroll in this study. Approximately 70 sites worldwide will participate in the study. Patients may continue allowed medications as background therapy provided they remain on stable doses throughout the Treatment Period.

1003157

Lexicon Pharmaceuticals, Inc.

LX1606.302

Final V1.0

Statistical Analysis Plan

4.2.1 Inclusion Criteria

Patients must meet all of the following criteria to be considered eligible to participate in the study:

1. Ongoing participation in a Phase 2 (e.g., LX1606.1-202-CS, LX1606.1-203-CS) or Phase 3 (e.g., LX1606.1-301-CS, LX1606.1-303-CS) study
2. Patients of childbearing potential must agree to use an adequate method of contraception (defined as having a failure rate of <1% per year) during the study and for 12 weeks after the Follow-up visit. Adequate methods of contraception for patients or partner include condoms with spermicide gel, diaphragm with spermicide gel, coil (intrauterine device), surgical sterilization, vasectomy, oral contraceptive pill, depot progesterone injections, progesterone implant, and abstinence during the study and for 12 weeks after the Follow-up visit.
 - a. Childbearing potential is defined as those who have not undergone surgical sterilization, or those who are not considered postmenopausal. Postmenopause is defined as absence of menstruation for at least 2 years. If necessary, follicle-stimulating hormone results > 50 IU/L at Baseline Day 1 are confirmatory in the absence of a clear postmenopausal history.
3. Ability and willingness to provide written informed consent prior to participation in any study-related procedure.

4.2.2 Exclusion Criteria

Patients who meet any of the following criteria will be excluded from participating in the study:

1. Major protocol deviations or telotristat etiprate tolerability concerns in a Phase 2 (e.g., LX1606.1-202-CS, LX1606.1-203-CS) or Phase 3 (e.g., LX1606.1-301-CS, LX1606.1-303-CS) study
2. Positive pregnancy test
3. Presence of any clinically significant findings at entry for medical history, laboratory values, or physical examination (relative to patient population) that, in the Investigator's or Medical Monitor's opinion, would compromise patient safety or the outcome of the study
4. Patients who are currently committed to an institution by virtue of an order issued either by judicial or administrative authorities

1003157

Lexicon Pharmaceuticals, Inc.

LX1606.302

Final V1.0

Statistical Analysis Plan

4.3 CRITERIA FOR STOPPING TREATMENT/STUDY WITHDRAWAL

A patient may also be discontinued from the study for the following medical or administrative reasons:

1. Withdrawal of consent by the patient or legal guardian
2. Noncompliance, including refusal of the study drug and/or failure to adhere to the study requirements as in the study protocol
3. Investigator decides that, in the interest of the patient, it is not medically acceptable to continue participation in the study
4. The Sponsor terminates the study
5. Pregnancy

4.4 CRITERIA FOR TERMINATION OF THE STUDY

If the Sponsor, Investigator, Study Monitor, DSMB, or regulatory officials discover conditions arising during the study that indicate that the patient safety and/or scientific value of the study and/or quality of the study drugs have been compromised, the study should be halted or the study center's participation should be terminated. Conditions that may warrant termination of the study include, but are not limited to, the following:

1. The discovery of an unexpected, serious, or unacceptable risk to the patients enrolled in the study
2. A decision on the part of the Sponsor to suspend or discontinue testing, evaluation, or development of the product for carcinoid syndrome or any other indication for any reason
3. Failure of the Investigator to enroll patients into the study at an acceptable rate
4. Failure of the Investigator to comply with pertinent governing body regulations
5. Submission of knowingly false information from the research facility to the Sponsor, study monitor, medical officer, or regulatory official
6. Insufficient adherence to protocol requirements

Lexicon Pharmaceuticals, Inc.
[name]
[name]

1003157

Lexicon Pharmaceuticals, Inc.

LX1606.302

Final V1.0

Statistical Analysis Plan

4.5 DETERMINATION OF SAMPLE SIZE

No formal sample size calculation was made. The number of patients expected to participate in this study was calculated from estimated enrollment rates from other trials of carcinoid syndrome employed in the LX1606 clinical program. Up to 100 patients are expected to enroll in this study.

4.6 TREATMENT ASSIGNMENT AND BLINDING

This is an open-label study. Patients will enter the study at the same dose level and regimen as identified in the prior Phase 2 or Phase 3 CS study. Randomization will not be used to assign patients to study treatments.

4.7 ADMINISTRATION OF STUDY DRUG

All patients will be instructed to take the telotristat etiprate with food. “With food” means taking telotristat etiprate tablets within 15 minutes before or within 1 hour after a meal or snack. Patients will be instructed to take study drug 3 times daily (tid) during waking hours, with doses spaced approximately 6 hours apart.

Study drug and instructions will be dispensed to patients at each visit as described in the schedule of study procedures ([Table 1](#)).

4.8 STUDY PROCEDURES

A schedule of study events is provided in [Table 1](#).

Statistical Analysis Plan

Table 1 Schedule of Events

Procedure	Extension Period								2-Week Follow-up ⁴
	Baseline Day 1 ¹	Week 12	Week 24	Week 36	Week 48	Week 60	Week 72	Week 84 / EOS	
Tolerance (days)	NA	± 5	± 5	± 5	± 5	± 5	± 5	± 5	± 5
Inclusion/Exclusion criteria	X								
Medical history	X								
Physical examination incl. weight	X	X ³	X ³	X ³	X	X ³	X ³	X	X ⁵
Urine pregnancy test ²	X	X	X	X	X	X	X	X	X
Hematology, Blood chemistry	X	X	X	X	X	X	X	X	X ⁵
Urinalysis	X				X			X	X ⁵
Chromogranin A	X				X			X	
Vital signs	X	X	X	X	X	X	X	X	X
ECG	X				X			X	X ⁵
Subjective Global Assessment	X	X	X	X	X	X	X	X	X
EORTC QLQ-C30 & GLNET21	X		X		X		X	X	
Sleep and Depression Assessment	X	X	X	X	X	X	X	X	X
Plasma 5-HIAA	X	X	X	X	X	X	X	X	X
Dispensation of LX1606	X	X	X	X	X	X	X		
Concomitant medications	X	X	X	X	X	X	X	X	X
Adverse events	X	X	X	X	X	X	X	X	X

¹Eligibility will be determined at last visit of the original protocol; Day 1 will replace the next scheduled visit in the original protocol schedule. Visits should coincide with LAR injections for those patients receiving SSA therapy. ²Females of child-bearing potential only. ³Brief physical examination only (symptom-oriented, including weight). ⁴Visit to be performed for subjects who withdraw early and will not return for a 2-week follow-up visit; in all other cases the EOS visit should be performed followed by the follow-up visit 2 weeks postdose. ⁵To be performed only if evaluation at Week 84/EOS is abnormal.

Statistical Analysis Plan

5 ENDPOINTS

5.1 EFFICACY ENDPOINTS

Efficacy endpoints are the long-term changes in patients' QoL, including:

- Change from Baseline in overall and domain scores of the European Organisation for Research and Treatment of Cancer QoL questionnaire (EORTC QLQ)-C30 and GI.NET21 at each study visit
- Proportion of patients that report adequate relief of CS symptoms at each study visit
- Change from Baseline in subjective global assessment of CS symptoms on an 11-point Numeric Rating Scale (NRS) at each study visit

5.2 PHARMACODYNAMIC ENDPOINT

The pharmacodynamic endpoint is the change from Baseline in plasma levels of 5-hydroxyindoleacetic acid (5-HIAA) at each study visit

5.3 SAFETY ENDPOINTS

Safety endpoints are as follows:

- Incidence of TEAEs, suspected adverse reaction, adverse events (AEs) leading to discontinuation from the study, serious AEs (SAEs), deaths, and AEs of special interest
- Actual and change from Baseline in clinical laboratory results
- Actual and change from Baseline in vital signs results
- Actual and change from Baseline in physical examinations
- Actual and change from Baseline in ECG findings

5.4 OTHER ENDPOINTS

Other endpoints are as follows:

- Chromogranin A (CgA) levels

1003157

Lexicon Pharmaceuticals, Inc.

LX1606.302

Final V1.0

Statistical Analysis Plan

- Disease progression
- Quality of sleep assessment

6 ANALYSIS POPULATIONS

The primary analyses of the data will be based on the safety population (SAF). Supportive analyses of the efficacy data will be performed on a per-protocol (PP) population.

6.1 ENROLLED POPULATION

The enrolled population includes all patients who sign the informed consent form. Unless specified otherwise, this population will be used for patient listings and for summaries of patient disposition.

6.2 PER-PROTOCOL POPULATION

The PP population will consist of those patients who receive telotristat etiprate and have no major protocol deviation(s) that would interfere with the collection or interpretation of the efficacy data. Patients with significant protocol deviations will be excluded from the PP population. Determination of the PP population will be made before database lock. The primary analyses of efficacy will be based on the SAF; the PP population will be used in a supplemental manner.

6.3 SAFETY POPULATION

The SAF consists of all patients receiving any fraction of a dose of telotristat etiprate during the study.

7 GENERAL ASPECTS FOR STATISTICAL ANALYSIS

7.1 GENERAL METHODS

Statistical methodology and analyses are in accordance with the principles outlined by the International Conference on Harmonisation (ICH) E9 guidelines^[1].

Patient listings of all data represented in the electronic case report form (eCRF) will be provided. Measurements from patients excluded from the predefined analysis populations or extra measurements (such as unscheduled or repeat assessments) will not be included in summary tables unless specified otherwise, but will be included in the patient listings. In general, the patient listings will be sorted by treatment group,

1003157

Lexicon Pharmaceuticals, Inc.

LX1606.302

Final V1.0

Statistical Analysis Plan

patient number, and assessment date (and time), if applicable. For most summary statistics, data will be analyzed and displayed by the order of the treatment groups and overall, where treatment groups correspond to how patients were dosed on Day 1 of this study.

Unless otherwise specified, continuous/quantitative variables will be summarized using descriptive statistics, which will include the number of patients with data to be summarized (n), mean, standard deviation (SD), median, minimum, and maximum. The same number of decimal places as in the raw data will be presented when reporting the minimum and maximum, 1 more decimal place than in the raw data will be presented when reporting the mean and median, and 2 more decimal places than in the raw data will be presented when reporting the SD.

All categorical/qualitative data will be presented using frequency counts and percentages. The total number of patients in the treatment group overall (N) will be used as the denominator for percentage calculations, unless stated otherwise in the table shell. All percentages will be presented as 1 decimal point, unless otherwise specified. Percentages equal to 100 will be presented as 100%, and percentages will not be presented for zero frequencies.

All statistical tests will be 2-sided and have an associated α -level = 0.05 unless mentioned otherwise. Confidence limits (CLs) will be 2-sided and calculated with a 95% confidence coefficient.

All statistical analyses will be done using SAS statistical software version 9.3 or higher.

In the case of multiple or repeat assessments at a scheduled visit, the latest value at the visit will be used for summarization and analyses.

7.2 KEY DEFINITIONS

7.2.1 Baseline Values

Day 1 of this study will serve as the baseline assessment. The Baseline value is defined as the last non-missing measurement or assessment for safety and efficacy parameters assessed on Day 1 of this study.

7.2.2 First Dose Date

The first dose date will be the date that the first dose of telotristat etiprate is administered during the study. The first dose date will be obtained from the eCRF.

1003157

Lexicon Pharmaceuticals, Inc.

LX1606.302

Final V1.0

Statistical Analysis Plan

7.2.3 Study Day

There is no study day 0. Study day for an event occurring prior to first dose date is defined as Event Date - First Dose Date. The study day for an event occurring on or after first dose date is defined as Event Date - First Dose Date + 1.

7.2.4 Last Dose Date

The last dose date will be the date that the last dose of telotristat etiprate was taken during the study. The last dose date will be obtained from the CRF.

7.2.5 Duration

Treatment duration in weeks will be determined as $\text{Duration} = (\text{Last Dose Date} - \text{First Dose Date} + 1) / 7$, rounding to 1 decimal place.

7.2.6 End of Study

The end of study (EOS) is defined as date of early termination or the date of completion of treatment for enrolled patients. It will be obtained from the eCRF. The EOS value is defined as the last non-missing measurement or assessment on or before the EOS.

7.3 MISSING DATA

There is no plan to impute data for missing observations for any variable.

7.4 HANDLING OF PARTIAL DATES

Complete dates will be imputed from partial dates of AEs and medications solely for the purpose of defining treatment emergence for AEs and prior/concomitant status for medications. Dates will be defined using the hierarchy of derivations below.

Adverse Events

- For missing start day where month and year are present, the start day will be set to the 1st of the month, unless the 1st of the month is before the first dose date, in which case, the start day will be set to the first dose date.
- For missing start day and month where year is present, the start day and month will be set to January 1st, unless January 1st is before the first dose date, in which case, the start day and month will be set to the first dose date.
- For missing end day where month and year present, the end day will be set to the last day of the month, unless the month is the trial termination month, in which case, the end day will be set to the trial termination date.

1003157

Lexicon Pharmaceuticals, Inc.

LX1606.302

Final V1.0

Statistical Analysis Plan

- For missing end day and month, where year is present, the end day and month will be set to the trial termination date, unless the trial termination year is greater than the end year, in which case, the end day and month will be set to December 31st.

Concomitant Medication

If the start date of a concomitant medication is missing, then the start date will be estimated using the first dose date. If the stop date of a concomitant medication is missing, then the medication will be treated as ongoing. Other non-complete dates will use the same algorithm as above for TEAEs.

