8.5.1 Prior Medications

All medications and other treatments taken by patients within 30 days prior to the Day 1 visit will be recorded on the eCRF. Prior medications are defined as medications taken prior to the first dose of telotristat etiprate. Partial date imputation for medications is described in [Section 7.4](#).

Prior medication use will be summarized by level 2 ATC and PT using the number and percentage of patients by treatment group. Medications will be sorted alphabetically by ATC and preferred name within ATC. Patients with multiple occurrences of a medication in ATC and preferred name will only be counted once within each ATC and preferred name.

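### Read literally, SAP 7.4 never imputes a partial medication start before the first dose, so drugs recorded as begun in an earlier month or year can drop out of the prior-medication table

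*SAP*

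**What the plan says.** SAP section 7.4 limits date imputation to two uses. It is done "solely for the purpose of defining treatment emergence for AEs and prior/concomitant status for medications".

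The start rules are written for adverse events:

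- Day missing: use the 1st of the month, with an exception that substitutes the first dose date ("unless the 1st of the month is before the first dose date, in which case, the start day will be set").
- Day and month missing: use January 1st, with the same substitution ("unless January 1st is before the first dose date, in which case, the start day and month will be set").

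The end rules are built differently. With the day missing, the last day of the month is used, "unless the month is the trial termination month, in which case, the end day will be set to the trial termination date". The year-only end rule likewise compares the recorded year with the year of trial termination.

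For medications, a wholly missing start has its own rule: "If the start date of a concomitant medication is missing, then the start date will be estimated using the first dose date". Everything else is handed to the adverse event rules: "Other non-complete dates will use the same algorithm as above for TEAEs".

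Section 8.5.1 gives the definition that this imputation serves: "Prior medications are defined as medications taken prior to the first dose of telotristat etiprate". The same section refers to 7.4 for incomplete dates ("Partial date imputation for medications is described in" Section 7.4), so the algorithm governs prior as well as concomitant medications. Section 8.5.2 defines concomitant medications as those taken on or after the first dose date.

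**The concern.** The exception in the start rules makes sense when the recorded month or year is that of the first dose. There the record cannot show on which side of the first dose the drug began, and a convention is needed. When the recorded month or year lies wholly before the first dose there is nothing to resolve: the drug began earlier. The text nevertheless applies the exception there too, because the 1st of any earlier month precedes the first dose date. The end rules have the matching check that the start rules lack, which suggests a drafting slip.

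For medications, prior or concomitant status is the only thing the imputation is meant to settle, and this is what the rule gets wrong. Patients come from parent studies and may continue background therapy (section 4.2), so drugs begun well before Day 1 are to be expected. At stake are the completeness of the prior-medication summary and the internal consistency of imputed start and stop dates.

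**Working it through.** The plan gives no figure to reproduce. The check is to apply the rule as written.

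**Rule as written.** Let C be the 1st of the recorded month, or January 1st if only the year is known. Let F be the first dose date. If C < F, start = F; otherwise start = C.

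**Direct consequence.** Either start = F, or start = C with C ≥ F. In both cases start ≥ F, so no partial start can be imputed before the first dose.

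**Comparison rule.** Start = F only if the recorded month and year (or the year, for year-only dates) equal those of F; otherwise start = C.

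**Worked records.** F is assumed to be 15 March 2014 and to coincide with Day 1. The stop dates fall 5 to 23 days before F. Section 8.5.1 has drugs taken in the 30 days before Day 1 recorded, so such records can occur.

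| Recorded start | Stop | Start as written | Start with same-month/same-year condition |
|---|---|---|---|
| Jan 2010 | ongoing | 15 Mar 2014, not prior | 1 Jan 2010, prior |
| 2009 | ongoing | 15 Mar 2014, not prior | 1 Jan 2009, prior |
| Jan 2014 | 5 Mar 2014 | 15 Mar 2014, after stop | 1 Jan 2014, prior |
| Feb 2014 | Feb 2014 (imputed 28 Feb) | 15 Mar 2014, after stop | 1 Feb 2014, prior |
| 2013 | 1 Mar 2014 | 15 Mar 2014, after stop | 1 Jan 2013, prior |
| Mar 2014 | 10 Mar 2014 | 15 Mar 2014, after stop | 15 Mar 2014, after stop |
| 2014 | 20 Feb 2014 | 15 Mar 2014, after stop | 15 Mar 2014, after stop |
| Apr 2014 | ongoing | 1 Apr 2014, not prior | 1 Apr 2014, not prior |

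The first five rows are wrong as written and are repaired by the condition. The sixth and seventh need a further limit, because the start must also not be imputed later than the stop.

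**Enumeration.** Pairing every first dose date in 2013 to 2015 (an assumed range) with every earlier month back to January 2000 gives 190,011 combinations. All 190,011 are moved to the first dose date. This confirms the logic above; it is not an estimate of how many records are affected.

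**Where the effect stops.**

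- Ongoing drugs are taken after the first dose whatever their start, so they stay correctly concomitant under 8.5.2.
- Section 9.2 treats every adverse event reported in this study as treatment-emergent, so the same rule does no harm there.
- No efficacy model in section 8.6 uses prior-medication status.
- Listings show missing parts of dates as dashes (14.2.5.3), so the recorded partial date remains visible.

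**The case against.** **The rule might replace only the missing parts.** The clauses speak of the start day, or the start day and month, being set. One could therefore keep the recorded month and year and borrow only the day from the first dose. January 2010 would become 15 January 2010, which is prior, and the first five rows of the table would come right. The reading is possible but strained: the text sets the start to the first dose date, not to its day of the month. Borrowing a day can also produce a date that does not exist, such as the 31st of a 30-day month. It leaves the last two stopped drugs wrong: the 2014 start with a stop on 20 February and the March 2014 start with a stop on 10 March both still become 15 March 2014. Two readings that give different prior status are also a reason to reword.

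**Drugs stopped before Day 1 will contaminate the concomitant table.** A reader might infer this from the impossible date pairs. The SAP does not support it. Sections 8.5.1 and 8.5.2 define status by when a drug was taken, and nothing says that the start date alone decides. A recorded stop before the first dose already shows prior and not concomitant use. The misplacement would follow only if a program read status from the imputed start alone.

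**A definite share of the prior-medication table is lost.** This too goes beyond the SAP, which does not say how often start dates are partial. Lost records are also not lost counts: each patient is counted once per ATC class and preferred term, so one record with a complete pre-dose start keeps the patient in that row.

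**Wholly missing starts are set to the first dose date as well.** That is an explicit convention which no recorded month or year contradicts. It is not part of this point.

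**The impact is small.** This stands. Section 9 names concomitant medications, not prior ones, among the sources for the safety evaluation, and the prior table is descriptive.

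**Conclusion.** The point holds in limited form. On the literal reading, the start rule in 7.4 overrides recorded information and denies prior status to any medication whose partial start lies in a month or year before the first dose, if status is read from the imputed date. Ongoing background drugs with such dates can be missing from the prior-medication table while appearing correctly in the concomitant table. A drug stopped before Day 1 can carry an imputed start after its stop.

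The size in this trial cannot be stated, because the number of partial start dates is not in the SAP. The calendar dates used in the check are assumptions, but the result does not depend on them: it holds for any first dose date and any earlier month.

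No safety or efficacy conclusion turns on this. It should still be corrected, because the rule fails at the one task it has for medications and the repair is trivial.

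**What to change.** Amend the start-date rules in section 7.4, at least as applied to medications:

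1. Day missing: use the first dose date only if the recorded month and year equal those of the first dose; otherwise use the 1st of the recorded month.
2. Day and month missing: use the first dose date only if the recorded year equals that of the first dose; otherwise use January 1st of the recorded year.
3. Never impute a start later than a known stop date.
4. Classify any medication with a stop before the first dose as prior only.

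Items 1 and 2 repair the earlier months and years. Items 3 and 4 repair the records in the first-dose month or year that those conditions leave wrong. The convention for wholly missing starts can stay, subject to items 3 and 4.

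The cost is a few words, one condition and one cap in the date derivation, and a rerun of the medication tables if they already exist. A note to file would do, as was used for the GI.NET21 scoring correction.
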